**Table 9: Individual rules (decision 1)**

Adverse Events Related to Trial Drug	Actiona
Moderate (Table 14) except QT interval prolongation, haematology, and liver function, for which rules are specified below)	Trial drug administration may be continued, delayed, temporarily suspended or discontinued in accordance with Investigator's clinical judgment
Moderate LFT increases: ALT or AST value $>3 \times$ and $<5 \times$ ULN	
QT interval prolongation: A prolongation of the uncorrected QT interval of greater than 500 ms, using consistent, technically valid triplicate ECG	Trial drug administration will be discontinued.
Haematology: a) Hb drop of $>25\%$ from baseline on Day-1 (only for values below the laboratory reference range), or to an absolute value of $<100\text{ g/L}$ b) Platelet count drop of $> 25\%$ from baseline on Day-1 (only for values outside the laboratory reference range), or absolute value of $<80 \times 10^9/\text{L}$ c) Clinically significant neutrophil drop b	
Severe (Table 14) except liver function, for which rules are specified below.	
ALT or AST value $>3 \times$ and $<5 \times$ ULN, and symptomatic or ALT or AST value $>5 \times$ ULN +/- symptoms b	
Serious (fatal or life-threatening)	
Serious LFT increase: ALT or AST value $>3 \times$ ULN together with bilirubin $>1.5 \times$ ULN, without other evidence of cholestasis	

aActions are only relevant for dosing regimens where additional doses are planned for administration.

bSymptoms include fatigue, nausea, vomiting, right upper quadrant pain or tenderness, fever, rash and/or eosinophilia (eosinophil percent or count above the ULN). Abbreviations: ALT: alanine aminotransferase; AST: aspartate aminotransferase; ECG: Electrocardiogram; Hb: Haemoglobin; ms: milliseconds; QT: QT interval; ULN: upper limit of normal.

\*Investigator judgement will be used to determine which of the pre-dose measurements are considered the baseline. Where possible, the baseline value should be the one that was taken at the closest time of day to the samples being assessed for change, to account for diurnal variation (for example, the D-1 morning blood samples)

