**Table 10: Cohort and trial rules (decisions 3 and 4)**

Adverse Events Related to Trial Drug	Reversibility	Number of Participants	Action a
Moderate LFT increases: ALT or AST value $>3 \times$ ULN and $<5 \times$ ULN	ALT/AST improves to $<3 \times$ ULN in all participants	$\geq 50\%$ of sentinel group $\geq 50\%$ of a treatment arm (if unblinded) $\leq 5$ participants of the remaining main cohort after sentinel dosing	Trial drug administration may continue
Moderate LFT increases: ALT or AST value $>3 \times$ ULN and $<5 \times$ ULN	ALT/AST does not improve to $<3 \times$ ULN in all participants	$\geq 50\%$ of sentinel group $\geq 50\%$ of a treatment arm (if unblinded) $\leq 5$ participants of the remaining main cohort after sentinel dosing	Further dosing of the remaining participants of the relevant treatment arm (if unblinded) or trial (if blinded) will be suspended. Re-commencement of dosing requires regulatory approval via a substantial amendment a Further dosing of the remaining participants of the relevant treatment arm (if unblinded) or trial (if blinded) will be suspended. Re-commencement of dosing requires regulatory approval via a substantial amendment a
QT interval prolongation: A prolongation of the uncorrected QT interval of greater than 500 msec, using consistent, technically valid triplicate ECG	N/A	$\geq 2$	
Haematology: a) Hb drop of $>25\%$ from baseline on Day -1 (only for values below the laboratory reference range), or to an absolute value of $<100\text{ g/L}$ b) Platelet count drop of $>25\%$ from baseline on Day -1 (only for values below the laboratory reference range), or absolute value of $<80 \times 10^9/\text{L}$ Clinically significant neutrophil drop b		$\geq 2$	
Severe Adverse Reaction (Table 14)		$\geq 2$	

Adverse Events Related to Trial Drug	Reversibility	Number of Participants	Actiona
Severe LFT increase: ALT or AST value $>3 \times$ ULN and symptomatic/ ALT or AST value $>5 \times$ ULN +/- symptoms b		$\geq 2$	
Serious Adverse Reaction (fatal or life-threatening)		$\geq 1$	
Serious LFT increase: ALT or AST value $>3 \times$ ULN, together with Bilirubin $>1.5$ ULN without other evidence of cholestasis		$\geq 1$	

aA substantial amendment may include an amendment to the protocol, the ICF, or other trial related documents as appropriate.

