Severe	Overall clinical condition is asymptomatic or is symptomatic with one or more of the following characteristics: 

• significant impact on usual self-care activities

• inability to perform usual social & functional activities

• the deviation from reference range for the population and from the participant's baseline has significant clinical impact, it is an acute safety concern or unanticipated risk and requires close and continuous monitoring

• the reversibility of the condition to baseline condition takes significantly longer than desirable or anticipated, with significant impact on the participant's wellbeing

• intervention or treatment essential to treat the acute manifestations and to prevent worsening

• life-threatening or actually leads to death.

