### **8.2.3 Practical application of severity grading and causality assessment in relation to AR rules**

**Step 1:** Confirm diagnosis of the AE/AR (exact term will be decided using the MedDRA), once the root cause of the clinical manifestations has been determined (rather than diagnosing individual signs, symptoms, assessments, and measurements).

**Step 2:** Distinguish between serious and non-serious AE/ARs using the standard definitions of what constitutes a 'serious' AE/AR (see Section 8.1).

**Step 3:** Assess whether there is a reasonable possibility of a relationship with the IMP.

**Step 4:** If there is a reasonable possibility that it is related to the IMP, apply the correct AR rules (see Section 4.4):

- '**serious AR**': The classification as 'serious' (see Sections 8.1 and 8.2) overrides the application of the categorical (mild/moderate/severe) grading system. The rules for serious AR must be applied. Categorical grading (moderate or severe) should also be independently recorded to add additional information.
- '**non-serious AR**':
  - some individual clinical manifestations, signs, symptoms, assessments, or measurements (such as QT prolongation, anaemia, thrombocytopenia, liver enzyme abnormalities) have pre-defined special AR rules, which should be applied if they occur
  - for all other non-serious ARs use the global clinical assessment and categorical grading method outlined above to assign the severity grade (Section 8.2). Consider:
    - the clinical significance (including presence or absence of clinical symptoms)
    - participant populations' specific references ranges and degree of deviations thereof
    - the degree of deviations from baseline
    - timing, duration, and reversibility

- the nature and intensity of treatment required and the responses to the treatment; in addition, the potential to worsen or to become defined as serious
- apply the general AR rules according to the assigned categorical severity grade.

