#### **8.2.5 Adverse Events of Special Interest (AESI)**

An 'AESI' is an Adverse Event of scientific or medical concern that is specific to the Sponsor or the particular product or program, for which ongoing monitoring and rapid communication by the Investigator to the Sponsor may be appropriate. It may require further investigation in order to be characterised and understood. It could be serious or non-serious and could include events that might be potential precursors or prodromes for more serious medical conditions in susceptible individuals. If an AESI is serious, reporting procedures for SAE/SUSAR will be used. For non-serious AESI, reporting procedures will be described in the SOM.

The AESIs for this protocol include, but are not limited to, the following:

- hepatic:
  - Moderate: any ALT or AST  $>3 \times$  and  $<5 \times$  ULN
  - Severe: any ALT or AST  $>3 \times$  and  $<5 \times$  ULN with symptoms/ ALT or AST  $>5 \times$  ULN with or without symptoms\*
  - Serious: ALT or AST  $>3 \times$  ULN together with an increase in bilirubin to  $>1.5 \times$  ULN
- cardiac:
  - uncorrected QT interval  $>500$  msecs, using consistent, technically valid triplicate ECG
  - second- or third-degree atrioventricular (AV) block
  - bundle branch block
  - any arrhythmia
- haematological:
  - Hb drop of  $>25\%$  from baseline on Day -1 (only for values below the laboratory reference range), or to an absolute value of  $<100$  g/L
  - platelet count drop of  $>25\%$  from baseline on Day -1 (only for values outside the laboratory reference range) or absolute value of  $<80 \times 10^9/L$ .
  - clinically significant drop from baseline in neutrophil count\*\*

\*symptoms include fatigue, nausea, vomiting, right upper quadrant pain or tenderness, fever, rash and/or eosinophilia (eosinophil percent or count above the ULN).

\*\*baseline refers to all samples taken prior to dosing on Day 1 (e.g. at screening, on Day -1).

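### The only mandatory numeric QT trigger is uncorrected QT above 500 ms, so above 60 bpm a QTcF over 500 ms can leave stopping to discretion

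*Protocol*

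**What the plan says.** **Stopping and special-interest rules.** Protocol Table 9 discontinues trial drug for "A prolongation of the uncorrected QT interval of greater than 500 ms, using consistent, technically valid triplicate ECG". Table 10 suspends dosing when two or more participants have "A prolongation of the uncorrected QT interval of greater than 500 msec" on the same kind of recording. Section 8.2.5 lists uncorrected QT above 500 "msecs, using consistent, technically valid triplicate ECG". None of the three gives a QTc value or a change from baseline.

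**Rest of the plan.** Exclusion criterion 10 (Protocol Section 5.4) uses QTcF above 450 ms. The ECG categories in Protocol Section 10.3 and SAP Section 4.11.6 use QTcF, with more than 500 ms as the top category.

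**Severity route.** The Moderate row of Table 9 excepts QT prolongation by name. The Severe row reads "Severe (Table 14) except liver function, for which rules are specified below", so QT is not excepted there. Table 10 has a general Severe row without exception. Table 14 allows an asymptomatic event to be Severe where "it is an acute safety concern or unanticipated risk and requires close and continuous monitoring". Section 8.2.3 Step 4 names QT prolongation among the findings that "have pre-defined special AR rules, which should be applied if they occur", and then says "for all other non-serious ARs use the global clinical assessment and categorical grading method outlined above to assign the severity grade".

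**Scope of the individual action.** Table 9 footnote a: "Actions are only relevant for dosing regimens where additional doses are planned for administration".

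**The concern.** Piperaquine (PQP) is a known QT prolonger, and Protocol Section 1 names QTc prolongation as one of three toxicities to watch. The protocol selects participants and describes ECG results on a rate-corrected scale, but its mandatory trigger is on an uncorrected one. Whether the trigger is met therefore depends on heart rate as well as on repolarisation.

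Above 60 bpm, a participant can reach the plan's own top QTcF category while no mandatory rule applies. The Moderate row does not cover QT prolongation, so the action depends on someone grading the event Severe or using another discretionary power.

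Two decisions are at stake: whether that participant receives a remaining dose, and whether the event counts towards the Table 10 limit of two before later participants are dosed.

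**Working it through.** **Inputs.** Trigger: uncorrected QT above 500 ms (Tables 9 and 10, Section 8.2.5). Top category: QTcF above 500 ms (Protocol Section 10.3, SAP Section 4.11.6). Entry heart rate: 40-100 bpm supine (exclusion criterion 11). Expected mean fasted effect of PQP: 15-20 ms (Protocol Section 1, safety and tolerability). ECG times: Table 6.

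The documents give no figure for how often the trigger and QTcF would disagree, so there is none to reproduce.

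**Formula.** The documents name Fridericia's correction without writing it out. Its standard form is QTcF = QT / RR^(1/3), with RR = 60/HR in seconds. Hence QT at QTcF 500 ms is 500 × (60/HR)^(1/3), and QTcF at QT 500 ms is 500 / (60/HR)^(1/3).

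Worked at 75 bpm: RR = 60/75 = 0.8 s and 0.8^(1/3) = 0.928. QTcF 500 ms is then a QT of 464.2 ms, and a QT of 500 ms is a QTcF of 538.6 ms.

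| HR (bpm) | QT when QTcF = 500 ms | QTcF when QT = 500 ms |
|---|---|---|
| 45 | 550.3 | 454.3 |
| 50 | 531.3 | 470.5 |
| 55 | 514.7 | 485.7 |
| 60 | 500.0 | 500.0 |
| 65 | 486.8 | 513.5 |
| 70 | 475.0 | 526.4 |
| 75 | 464.2 | 538.6 |
| 80 | 454.3 | 550.3 |
| 100 | 421.7 | 592.8 |

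**Reading the table.** Above 60 bpm, the rule is not met for any QTcF between 500 ms and the value in the last column. Equivalently, a QTcF of 520 ms does not meet it above 60 × (520/500)^3 = 67.5 bpm, and 550 ms does not above 60 × (550/500)^3 = 79.9 bpm. Below 60 bpm the order reverses, and the rule acts at QTcF values under 500 ms.

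**How far from entry.** From the entry limit of 450 ms, a QTcF above 500 ms needs a rise of more than 500 − 450 = 50 ms, against an expected mean effect of 15-20 ms.

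**When the rule can act.** Scheduled ECG time points after dose 1 and before dose 3:
- Day 1 post-dose: 9 (1 to 8 h, and 12 h)
- Day 2 pre-dose: 3
- Day 2 post-dose: 3 (4, 6 and 12 h)
- Day 3 pre-dose: 4

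The total is 9 + 3 + 3 + 4 = 19. The 9 post-dose time points on Day 3, when Section 1 expects the largest effect, cannot stop a dose in that participant. In a sentinel participant they can still count towards the Table 10 limit.

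**The case against.** **The Severe route is open.** Table 9 removes QT prolongation from the Moderate row by name but removes only liver function from the Severe row, and the general Severe row of Table 10 has no exception. A natural reading of Section 8.2.3 Step 4 is that QT prolongation short of the special criterion falls among the other reactions and is graded under Table 14. This largely stands. A reader might infer that Section 8.2.3 closes the Severe route. The tables do not support that; Step 4 is only loosely worded.

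**Other safeguards exist.** Every ECG is reviewed by a physician (Section 7.9.2), and telemetry is monitored (Section 7.9.4). The investigator may withdraw a participant for an adverse event (Section 5.6). The SRC considers all clinically significant findings (Table 8) and can meet ad hoc (Section 4.3.1). The special-interest list is not exhaustive (Section 8.2.5). Table 7 allows cardiologist referral and extra PK samples paired with ECGs. This also stands, so it would be wrong to infer that a participant with QTcF above 500 ms is unprotected. None of these safeguards makes a QTcF value a mandatory trigger.

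**The size is illustrative.** The 40-100 bpm range is an entry criterion, not an on-treatment distribution. At 65 bpm the gap is about 13 ms. Below 60 bpm the present rule is stricter, so it cannot be called laxer throughout. Nor do the documents fix a direction of heart-rate change: Table 3 links PQP to tachycardia and pyronaridine to bradycardia.

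**Timing.** SAP Section 3.2 says recruitment stopped at 37, and the note to SAP Figure 1 describes the in-house stay in the past tense. A rule change would do little for this trial. This stands and lowers the priority.

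**Conclusion.** The point holds as a minor one. The only mandatory numeric QT trigger is uncorrected, and above 60 bpm it can remain unmet at QTcF above 500 ms, for example with QT between 464 and 500 ms at 75 bpm. Stopping then depends on a Severe grade, withdrawal for an adverse event, or SRC review.

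The event should be uncommon, given the entry limit (apart from agreed borderline cases) and the expected mean effect. The conclusion rests on the standard Fridericia exponent and on illustrative heart rates. Without an on-treatment heart-rate distribution no probability can be given.

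A reader might infer that some participants in this trial were dosed past a threshold that should have stopped them. The documents contain no results and do not support that.

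**What to change.** In Tables 9 and 10 and Section 8.2.5, make the criterion uncorrected QT above 500 ms **or** QTcF above 500 ms, under the existing condition of consistent, valid triplicate recordings. Keep the unconditional discontinuation in Table 9. Do not make the trigger subject to clinical confirmation, because that could soften the present rule for uncorrected QT. Retaining the uncorrected limb keeps the stricter behaviour below 60 bpm.

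In Section 8.2.3 Step 4, add that QT prolongation not meeting the special rule is still graded under Table 14 and can fall in the Severe row.

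The cost is three short edits and one sentence, with possibly a few more individual or trial stops because either measure would trigger. The change applies to any further dosing under these rules.

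A SAP table row counting participants with uncorrected QT above 500 ms is optional and not part of this point. It would not match the protocol criterion exactly, since that criterion also requires relatedness and consistent triplicates, and SAP Section 4.1 limits summary tables to scheduled time points.

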**Table 10: Cohort and trial rules (decisions 3 and 4)**

Adverse Events Related to Trial Drug	Reversibility	Number of Participants	Action a
Moderate LFT increases: ALT or AST value $>3 \times$ ULN and $<5 \times$ ULN	ALT/AST improves to $<3 \times$ ULN in all participants	$\geq 50\%$ of sentinel group $\geq 50\%$ of a treatment arm (if unblinded) $\leq 5$ participants of the remaining main cohort after sentinel dosing	Trial drug administration may continue
Moderate LFT increases: ALT or AST value $>3 \times$ ULN and $<5 \times$ ULN	ALT/AST does not improve to $<3 \times$ ULN in all participants	$\geq 50\%$ of sentinel group $\geq 50\%$ of a treatment arm (if unblinded) $\leq 5$ participants of the remaining main cohort after sentinel dosing	Further dosing of the remaining participants of the relevant treatment arm (if unblinded) or trial (if blinded) will be suspended. Re-commencement of dosing requires regulatory approval via a substantial amendment a Further dosing of the remaining participants of the relevant treatment arm (if unblinded) or trial (if blinded) will be suspended. Re-commencement of dosing requires regulatory approval via a substantial amendment a
QT interval prolongation: A prolongation of the uncorrected QT interval of greater than 500 msec, using consistent, technically valid triplicate ECG	N/A	$\geq 2$	
Haematology: a) Hb drop of $>25\%$ from baseline on Day -1 (only for values below the laboratory reference range), or to an absolute value of $<100\text{ g/L}$ b) Platelet count drop of $>25\%$ from baseline on Day -1 (only for values below the laboratory reference range), or absolute value of $<80 \times 10^9/\text{L}$ Clinically significant neutrophil drop b		$\geq 2$	
Severe Adverse Reaction (Table 14)		$\geq 2$	

Adverse Events Related to Trial Drug	Reversibility	Number of Participants	Actiona
Severe LFT increase: ALT or AST value $>3 \times$ ULN and symptomatic/ ALT or AST value $>5 \times$ ULN +/- symptoms b		$\geq 2$	
Serious Adverse Reaction (fatal or life-threatening)		$\geq 1$	
Serious LFT increase: ALT or AST value $>3 \times$ ULN, together with Bilirubin $>1.5$ ULN without other evidence of cholestasis		$\geq 1$	

aA substantial amendment may include an amendment to the protocol, the ICF, or other trial related documents as appropriate.

bSymptoms include fatigue, nausea, vomiting, right upper quadrant pain or tenderness, fever, rash and/or eosinophilia (eosinophil percent or count above the ULN).

Abbreviations: ALT: alanine aminotransferase; AST: aspartate aminotransferase; ULN: upper limit of normal; QT: QT interval; ms: milliseconds; ECG: electrocardiogram; Hb: haemoglobin; SOC: System Organ Class; WCC: white cell count.

The investigators judgement will be used to determine which of the pre-dose measurements are considered the baseline. Where possible, the baseline value should be the one that was taken at the closest time of day to the samples being assessed for change, to account for diurnal variation (for example, the D-1 morning blood samples).

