#### **1.2.2.2 Pyronaridine (PYR)**

Transient ALT/AST elevations above 3 x ULN are commonly reported in clinical trials investigating the three-day regimen of PYR-AS (pyronaridine-artesunate, Pyramax®). These elevations have been reported in both patients treated for acute uncomplicated malaria and healthy participants enrolled in clinical pharmacology studies. The overall pattern seems consistent across studies with a transient asymptomatic elevation in ALT/AST without bilirubin elevation which for most of the episodes occurred after the three-day treatment, within three and seven days after the initial dose and resolved within 21 days after reaching a peak value between eight and fifteen days after the first day of treatment. Higher elevations of >10 x ULN in patients and >5 x ULN in healthy have also been reported but are less common.

Concomitant elevation in bilirubin and possible Hy's Law cases have not been reported in healthy participants. In a retrospective pooled analysis of completed trials in patients, a total of 16 cases defined as concomitant elevations in ALT or AST >3 x ULN and total bilirubin >2xULN (i.e. Hy's Law cases) were reported in the clinical development program for PYR-AS. Ten cases were reported in malaria patients receiving PYR-AS and six were also reported in patients receiving one of the comparator malaria drugs which could possibly suggest a confounding background effect of the disease. Of these 16 cases, the Independent Safety

---

Monitoring Board adjudicated six possible Hy's Law cases in the PYR-AS group and four in the comparator drugs group.

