A total of four Phase 1 studies were conducted with PYR-AS in healthy participants. A SAD-MAD-Food Effect study was conducted in healthy South Korean participants [21] and three subsequent clinical pharmacology studies including a human C14 study were performed in Switzerland [22,23,24]. With the exception of the human ADME study where PYR was administered as a single oral dose, all these Phase 1 studies have evaluated the three-day therapeutic regimen of PYR-AS for acute uncomplicated malaria. Of note, the safety laboratory tests monitoring in the Asian study was limited to two post-dose time-points (72h and Day 11) while the two other studies (both DDI studies) used a very intensive monitoring with almost daily for one week and then weekly ALT/AST/bilirubin evaluations up to study end which covered a full month of observation. In the two DDI studies with ritonavir and metoprolol the LFT monitoring obtained for the control arm (i.e. PYR-AS alone) showed ALT/AST elevations with normal bilirubin consistent with the pattern described in malaria patients [22,23]. For example, in the Metoprolol DDI study, the control group of Caucasian participants dosed with PYR-AS alone over three days in Period 1 showed the following incidence of asymptomatic ALT elevations: 37 % (1-3 x ULN), 3 % (3-5 x ULN) and 10 % (>5 x ULN, including one case >20 x ULN). Similar incidences were observed for AST with 3 % of the study participants reaching values in the range 10-20 x ULN [23]. In the MAD study conducted in South Korea with four incremental doses of PYR-AS, only one case of ALT/AST elevations (>2 x ULN) was reported. However, these results should be interpreted with caution due to the very limited number of timepoints for safety laboratory tests: the study schedule did not include ALT/AST/bilirubin evaluation between Day 4 and Day 11. Additionally, a statistical comparison conducted on ALT/AST changes from baseline to Day 4 or to Day 11 in this Phase 1 study showed a statistically significant increase in ALT/AST suggesting a trend for elevation versus placebo particularly at the two highest doses of PYR 12 and 15 mg/kg [21].

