**Table 7: Adaptive protocol features**

Adaptive Study Design Areas	Features	Limits
Sentinel/ subgroup dosing	1. Cohorts may be split into sub-groups.	
I. A mandatory sentinel dosing strategy of dosing four participants from treatment arm 1, and two participants from each of treatment arms 2, 3 and 4, will be used. There will be a total of ten participants in the sentinel dosing. The remaining participants can be dosed if safety and tolerability data up to 15 days post first dose is acceptable.
 
II. The participants in the sentinel group will all be dosed in parallel. If they are successfully dosed (i.e. it is deemed safe to dose the other participants), the remaining 30 participants may all be dosed at the same time, in parallel, or they may be divided into two or more dosing groups, with the groups being dosed on different days. Each dosing group would contain a minimum of two participants from each of the four treatment arms, to maintain blinding and avoid bias (See Table 12).

Flexible Cohort Sizes	2. Withdrawn participants can be replaced at the discretion of the sponsor and PI. 3. Replacement participants may be enrolled in an ongoing treatment group or dosed together as a group or dosed separately, except for	
I. The maximum extension is 100 % of the original treatment group.
 
II. Trial specific AR rules (Section 4.4) apply.

Adaptive Study Design Areas	Features	Limits
	
those participants in the sentinel group.
 
4. The number of participants in a treatment group can be extended to gather further information.
	

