#### **4.4 Adverse Reaction (AR) rules**

An AR is any AE where there is a reasonable possibility of it being related to the IMP(s). ARs will be classified in accordance with Sections 8.1 and 8.2 to support standardised recording and reporting.

- Seriousness will be assessed using the criteria in Section 8.1.
- Severity and causality will be assessed using the criteria in Section 8.2.

Seriousness and severity are assessed independently. 'Severity' characterises the intensity of an AE. 'Serious' is a regulatory definition and serves to define and trigger regulatory reporting obligations.

Seriousness and severity grade both have consequences when applying AR rules. Seriousness of an AR always overrides the severity grade and the rules for Serious AR should be applied, irrespective of severity grade.

**These rules will only apply to AEs/SAEs where there is a reasonable possibility of relationship to the IMP (i.e. ARs and SARs).** Every AE will be assessed in the following order:

- 1) the impact on the individual participant, e.g. whether IMP administration can be continued
- 2) whether blinding can continue for the individual
- 3) a) (if the participant is unblinded) the impact on the treatment arm the individual participant is part of, e.g. in the following circumstances:
  - o if a treatment arm is due to receive further doses (i.e. a dose on the following day), whether that treatment arm can receive further doses as per the dosing schedule
  - o if the individual(s) is/are part of the sentinel group, the impact on the successive participants of that treatment arm – i.e. whether the remaining subjects can be dosed or not.
- 3) b) (if the participant remains blinded) the impact on all remaining participants in the study, e.g. in the following circumstances:
  - o if participants are due to receive further doses (i.e. a dose on the following day), whether the remaining participants can receive further doses as per the dosing schedule
  - o if the individual(s) is/are part of the sentinel group, the impact on all successive participants – i.e. whether the remaining cohort can proceed or not.
- 4) the impact on continuation or suspension of the overall study.

The individual (decision 2), within-cohort (decision 3) and the trial progression (decision 4) rules are shown in Table 9 and Table 10 below.

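### Protocol Table 10, row 2: the main-cohort count that suspends dosing for non-reversing moderate ALT/AST rises is printed as an upper bound (≤5), so one case meets it and six do not

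*Protocol*

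**What the plan says.** Protocol Table 10 sets the cohort and trial rules. Its first two rows both deal with moderate rises (ALT or AST between 3 and 5 x ULN) and list the same three counts: ≥50% of the sentinel group, ≥50% of a treatment arm if unblinded, and ≤5 "participants of the remaining main cohort after sentinel dosing". No connecting word is printed between the three lines.

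- Row 1 applies when all the rises come back below 3 x ULN. Dosing may go on.
- Row 2 applies when they do not. Dosing of the arm (if unblinded) or of the whole trial (if blinded) is suspended, and "Re-commencement of dosing requires regulatory approval via a substantial amendment".

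The remaining suspension counts are ≥2 for QT, haematology and severe reactions, ≥2 for the row that begins "Severe LFT increase: ALT or AST value", and ≥1 for the two serious rows.

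For the affected individual, Table 9 says of moderate liver rises: "Trial drug administration may be continued, delayed, temporarily suspended or discontinued", according to the investigator's judgement. Section 4.4 gives the sequence of decisions: "Every AE will be assessed in the following order". Neither that section nor its tables set a time by which improvement must be shown.

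Amendment 02 (Reason for amendment, item 4) reversed the sign on the 50% lines of these two rows, as a drafting error. It lists no change to the line that counts five participants.

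**The concern.** An upper bound is the wrong form for a suspension trigger. One case satisfies it, and a sixth takes the count outside it. Had the sponsor wanted any single case to suspend, the natural entry would be ≥1, as in the serious rows.

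As printed, the order of severity is also upset: one asymptomatic moderate rise stops the blinded trial, while a rise above 5 x ULN, or a symptomatic one above 3 x ULN, needs two participants.

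Liver toxicity is one of the three toxicities that Section 1 names as its focus, so the SRC may well have to apply this row. The time course makes that more likely. Section 1.2.2.2 says that pyronaridine rises mostly "resolved within 21 days after reaching a peak value between eight and fifteen days after the first day of treatment". With no deadline for improvement, an ordinary transient rise could still count as not improved when it is reviewed. The cost would be an unnecessary halt and a substantial amendment to restart.

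**Working it through.** **1. The plan's own figure.** Table 10 has no stated operating characteristics. The only computable probability is in Protocol 10.7: at least one event in 16 combination participants. 1 − 0.90^16 = 81.5% (stated 81%) and 1 − 0.80^16 = 97.2% (stated 97%). Both reproduce.

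**2. What each count triggers.** This is the smallest main-cohort count that suspends a blinded trial, with the count lines read as alternatives.

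| Row | As printed | With ≥5 | With >5 |
|---|---|---|---|
| Moderate, non-reversing | 1 (and none above 5) | 5 | 6 |
| Severe LFT | 2 | 2 | 2 |
| Serious LFT | 1 | 1 | 1 |

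**3. Who has been dosed while doses remain.** Main cohort by arm: 16−4, 8−2, 8−2, 8−2 = 12, 6, 6, 6, total 30. On pyronaridine: 12 + 6 = 18. Table 7 allows all 30 to be dosed together, "or they may be divided into two or more dosing groups, with the groups being dosed on different days", with at least two participants per arm in each group. Each group therefore holds at least 4 pyronaridine participants. Between 4 and 18 − 4 = 14 have been dosed before the last group starts.

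**4. Rates.** Section 1.2.2.2 reports that a control group on pyronaridine-artesunate alone "showed the following incidence of asymptomatic ALT elevations: 37 % (1-3 x ULN), 3 % (3-5 x ULN"), and 10% above 5 x ULN. I take these as mutually exclusive per-participant rates, applying to the pyronaridine arms only. The share of moderate rises judged non-reversing is not given, so I assume 10% to 100%. That gives m = 0.003 to 0.03 for moderate non-reversing rises and s = 0.10 for severe ones.

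**5. Chance that the printed line is met.** This is 1 − (1 − m)^n.

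- n = 4: 1 − 0.997^4 = 1.2%; 1 − 0.97^4 = 11.5%.
- n = 14: 1 − 0.997^14 = 4.1%; 1 − 0.97^14 = 34.7%.

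**6. Suspensions that the line adds.** The severe row, which is not in dispute, would stop some of these trials anyway. The chance of two or more severe cases is 1 − 0.9^n − n(0.1)(0.9)^(n−1), which is 5.2% at n = 4 and 41.5% at n = 14. The added part is at least one moderate non-reversing case with at most one severe case:

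[0.9^n + n(0.1)(0.9)^(n−1)] − [(0.9 − m)^n + n(0.1)(0.9 − m)^(n−1)]

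| n | m = 0.003 | m = 0.03 |
|---|---|---|
| 4 | 0.9477 − 0.9361 = 1.2% | 0.9477 − 0.8363 = 11.1% |
| 14 | 0.5846 − 0.5591 = 2.6% | 0.5846 − 0.3713 = 21.3% |

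**7. A threshold of five.** At n = 14 and m = 0.03, the chance of five or more cases is 0.004% and of six or more 0.0002%. At n = 4 both are zero.

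**The case against.** The strongest reply is that the error is on the safe side and small in practice. Much of this stands.

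- **Timing.** The figures in step 6 need the rises to appear and be judged non-reversing before the last group finishes dosing. Table 7 gives no spacing between groups. Section 1.2.2.2 puts most onsets three to seven days after the first dose, with peaks on days 8 to 15. With groups a day or two apart, or all 30 in parallel, the added chance falls towards zero. The 1.2% is therefore not a floor.
- **No printed conjunction.** If the three count lines all had to hold, one main-cohort case would not be enough. They describe different populations, so alternatives are the natural reading, but the conclusion depends on it.
- **Table 9.** It leaves dosing of the affected person to judgement, which makes the trial rule look stricter than the individual rule. The comparison is loose: Table 9 does not condition on reversibility, and it applies only while that person has doses left.

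Three stronger readings are tempting, and the documents do not support them.

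- A reader might infer that a safety stop is missing at six or more cases. The row does have that gap. But Section 4.4 has each event assessed as it arises, so it opens only if six or more are first judged non-reversing at one review. The severe and serious rows remain, as do ad-hoc SRC review, possible unblinding of the cohort and the most-cautious default in Section 4.3.1.
- A reader might infer that row 1 is inverted too. There, ≤5 makes sense as a ceiling on continuing.
- A reader might take Amendment 02 as proof of what was meant. It shows that the same kind of slip occurred in the same cells. It does not settle between ≥5 and >5, nor exclude a missing further row.

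**Conclusion.** The row 2 main-cohort line is wrong as written and should be corrected. Read literally, with the count lines as alternatives, one asymptomatic non-reversing moderate rise judged related to the drug suspends the blinded trial. This conclusion rests on the wording and does not need the probabilities.

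The practical effect is an over-cautious stop. The size to quote is the added one in step 6. The 34.7% in step 5 would overstate it, because it counts trials that the severe row would have stopped anyway. The estimates rest on ALT rates from Caucasian participants on pyronaridine-artesunate, on an assumed non-reversing share, on planned numbers, and on groups spaced widely enough for rises to be seen and reviewed. Rates on the combination may differ.

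SAP 3.2 says that recruitment stopped at 37, and the SAP's flow-chart note describes the in-house stay in the past tense. Neither states that dosing is complete. A reader might suspect that this rule caused the shortfall from 40, but nothing in the documents says so.

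**What to change.** Change the row 2 main-cohort line to a lower bound: ≥5, or >5 if five cases are to be tolerated. State that the three count lines are alternatives. The sponsor should confirm the number as well as the sign, because at a 3% rate a threshold of five would almost never be reached before the last group. Leave row 1 as it is, apart from a check that it does not conflict with the corrected row 2.

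The cost is a text correction and a sponsor decision, with no effect on sample size, procedures or the SRC schedule. The downside is a less strict rule at 1 to 4 cases (1 to 5 with >5), where Table 9, the severe and serious liver rows and SRC review still apply. Because of that loosening, the sponsor should decide whether the amendment is substantial.

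If dosing is already complete, a sentence in the CSR stating which reading was applied is enough.
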